3.3.5 Discontinuation of subjects from treatment or assessment

3.3.5.1 Criteria for discontinuation

Subjects may be discontinued from study treatment and assessments at any time. Specific reasons for discontinuing a subject from this study are:

- Voluntary discontinuation by the subject, who are at any time free to discontinue their participation in the study without prejudice to further treatment
- Safety reasons as judged by the investigator and/or AstraZeneca including moderate to severe dyspnea that does not resolve or return to subject's baseline within 2 weeks.
- Severe non-compliance to protocol as judged by the investigator and/or AstraZeneca.
- Incorrect enrollment (ie, the subject does not meet the required inclusion/exclusion criteria) or randomization (ie, the subject is not allocated study drug as described in the protocol) of the subject.
- Subject lost to follow-up
- A suspected/manifested infection according to WHO risk categories 2, 3, and 4 (Refer to Appendix D).

3.3.5.2 Procedures for discontinuation

Subjects who discontinue should always be asked about the reason(s) for their discontinuation and the presence of any adverse events. If possible, they should be seen and assessed by an investigator(s). Adverse events should be followed up.

If a subject is being withdrawn due to a suspected infection in WHO risk categories 2, 3, and 4, no biological samples from this subject are allowed to be sent to the laboratory. Samples will be destroyed according to normal routines at the study site.

3.3.5.3 Procedures for Discontinuation from Genetic aspects of the study

Subjects who discontinue from the study should always be asked specifically whether they are withdrawing or continuing their consent for the linked genetic research. It must be established whether the subject:

- agrees to the genetic sample and any DNA extracted from the sample being kept for genetic analyses in the future.
- withdraws consent for the sample to be kept for genetic analysis in the future and wishes the sample to be destroyed. Destruction of the sample (or the DNA extracted from the sample) will only be possible so long as the particular sample is traceable. In the event that DNA analysis has already been performed, AstraZeneca will retain the results and associated data for regulatory reasons but these will not be used in any subsequent analyses.

The principal investigator is responsible for providing written notification to AstraZeneca of any subject who has withdrawn consent for the use of the sample taken for genetic analyses. AstraZeneca will provide written confirmation to the investigator of the actions taken with the sample, which must be filed in the investigator study file.

The appropriate process will be that the investigator contacts the study site monitor in the first instance, and then the study the monitor will forward this notification at the earliest possible opportunity to the head of the Clinical Genotyping Group (CGG). The CGG group will provide a written confirmation of the actions taken. The address of the CGG group is: Clinical Genotyping Group (CGG), [name], [contact], [contact].

3.4 Treatment(s)

AstraZeneca R & D Charnwood will supply all AZD6140 tablets and AZD6140 placebo-matching tablets. The investigator or institution has the responsibility to establish a system for handling study treatments, including investigational medicinal products, so as to ensure that:

1. Deliveries of such products from AstraZeneca Investigational Product (IPS) are correctly received by the investigator or his designee.
2. Such deliveries are recorded on the drug log.
3. Study treatments are handled and stored safely and properly.
4. Study treatments are only dispensed to study subjects in accordance with the protocol

5. Unused products are accounted for and returned to designated facility or AstraZeneca for destruction

3.4.1 Investigational Product(s)

3.4.1.1 Identity of investigational product

Table 4 Identity of Investigational Product

Investigational product	Dosage form and strength	Manufacturer	Formulation Number	Ingredients
AZD6140	90 mg immediate release tablets	AstraZeneca R & D Charnwood, UK	307	AZD6140, Mannitol, Dibasic calcium phosphate, Povidone K30 (PVP K30), Croscarmellose sodium, Magnesium stearate. Film coat: Hydroxypropyl methylcellulose 2910, titanium dioxide, lactose monohydrate, polyethylene glycol 3000, triacetin, iron oxide red, iron oxide yellow, iron oxide black
AZD6140 Placebo	Tablet, containing zero active therapy (identical in appearance to active tablets)	AstraZeneca R & D Charnwood, UK	234	Lactose monohydrate, Microcrystalline cellulose, Magnesium stearate Film coat: Hydroxypropyl methylcellulose 2910, titanium dioxide, lactose monohydrate, polyethylene glycol 3000, triacetin, iron oxide red, iron oxide yellow, iron oxide black

3.4.1.2 Labelling

AZD6140 and placebo-matching AZD6140 will be packed in individual wallet cards and labelled with randomization number and period for dosing. Each wallet card will contain a blister pack containing 21 tablets (overage included) of AZD6140 or placebo with a detachable tear-off label. Wallet cards labeled for Period I and Period II will be packed into a carton labelled with a single panel label.

The supplies will be labelled with the following information in accordance with Good Manufacturing Practice (GMP) and local regulatory requirements:

- **name of sponsor and address**
- **randomization number**

- **product name, dosage form, and quantity of dosage units**
- **Period I or II**
- **directions for use**
- **storage conditions**
- **lot number**
- **Keep out of reach of children**
- **Caution: New Drug - Limited by Federal (or USA) Law to Investigational Use**

3.4.1.3 Storage

All investigational products must be kept in a secure place under appropriate storage conditions. A description of the appropriate storage and shipment conditions are specified on the investigational product label and investigator brochure.

3.4.1.4 Accountability

The investigator (or delegate) is responsible for maintaining drug accountability records for study drugs. Drug accountability for this study will be carried out in accordance with standard procedures at the study center.

The medication provided for this study is for use only as directed in the protocol. Investigational site personnel or the AstraZeneca monitor will return all unused drugs to a vendor delegated by the sponsor. The investigational site personnel will account for all drugs dispensed and returned. Certificates of delivery and return must be signed.

3.4.2 Doses and treatment regimens

Each subject will receive each of the following treatments in one of two treatment sequences (AB or BA) according to the randomization schedule:

Treatment A: A single, oral dose of 450 mg AZD6140 (5 x 90 mg immediate release tablets) will be administered in the AM of Study Day 1; followed by a single, oral dose of 180 mg AZD6140 (2 x 90 mg immediate release tablet) in the PM (12 hours after the first dose); thereafter, 180 mg AZD6140 (2 x 90 mg immediate release tablet) will be administered bid (every 12 hours) on Study Days 2 and 3 and in the AM only on Study Day 4.

Treatment B: A single, oral dose of AZD6140 matching placebo (5 placebo tablets) will be administered in the AM of Study Day 1; followed by a single, oral dose of AZD6140 matching placebo (2 placebo tablets) in the PM (12 hours after the first dose); thereafter, AZD6140 matching placebo (2 placebo tablets) will be administered bid (every 12 hours) on Study Days 2 and 3 and in the AM only on Study Day 4.

All doses given in each treatment will be administered with 240 mL of room temperature water while the subject is sitting in an upright or in a semi-recumbent position. Subjects must remain either sitting or semi-recumbent for at least 2 hours after each dose intake.

On Study Days 1 and 4 of each treatment, the subjects will receive the AM study medication following an overnight (10 hour) fast and will continue to fast for 4 hours post dose. The PM

dose on Study Days 1, 2 and 3 will be given either 1 hour before or 1 hour after food intake. On Study Day 2 and 3, breakfast will be served 1 hour after the AM study medication.

3.4.3 Method of assigning subjects to treatment groups

Written informed consent will be obtained before enrollment and the volunteers identified with an enrollment number starting with E0001001. Subjects fulfilling the eligibility criteria will be assigned subject numbers starting with either number **101** (Cohort A), **201** (Cohort B) or **301** (Cohort C).

Using the AZ Global Randomization system (Grand) by AstraZeneca LP, volunteers treatment will be allocated as generated by the system.

Cohort	Volunteer Type	Randomization Number
A	Healthy Volunteers	101, 102, 103, 104, etc.
B	Mild Asthma	201, 202, 203, 204, etc.
C	Mild COPD	301, 302, 303, 304, etc.

Subjects will be randomized strictly sequentially within their Cohort as subjects are eligible for randomization on Day 1 of Period I before study drug administration. If a subject should be incorrectly randomized, randomization should continue with no attempt to correct the error. If a subject discontinues from the study, the randomization number will not be re-used and the subject will not be allowed to re-enter the study. Subjects who withdraw after having received study medication may be replaced by a subject who will be assigned to the same treatment sequence.

Each treatment group will consist of the same combination of matching active and placebo tablets. There will be four additional individual drug packages supplied for each cohort in the event of misrandomization, early withdrawal, etc. These will be used only as back-up and not for over enrolling subjects.

3.4.4 Blinding and procedures for unblinding the study

3.4.4.1 Methods for ensuring blinding

The treatment allocation in this study will be double-blind. The active study medication or placebo assignment will be blinded to both the subjects and to the investigator. To ensure the blinding of the treatments, matching AZD6140 placebo will be provided. Packaging, labelling and preparation of investigational products will be performed in a way that will ensure the blinding throughout the study. Neither the sponsor's representative responsible for monitoring the study, the study personnel, nor the investigator will know whether study drug or placebo has been allocated.

3.4.4.2 Methods for unblinding study

Individual treatment codes, indicating the treatment randomization for each randomized volunteer, will be available to the investigator or pharmacist at the study center.

The individual treatment codes must not be broken except in medical emergencies when the appropriate management of the volunteer necessitates knowledge of the treatment randomization. The investigator must document and report to AstraZeneca any breaking of the treatment code. AstraZeneca retains the right to break the code for SAEs suspected to be causally related to an investigational product and that potentially require expedited reporting to regulatory authorities.

Treatment codes will not be broken for the planned analyses of data until all decisions on the evaluability of the data from each individual subject have been made and documented.

The decision to dose the next cohort will be made following the review of the safety variables and without breaking of the study blind by the investigator and study team.

3.4.5 Concomitant medication

All subjects should refrain from taking any of the following medications:

1. prescribed medication from 4 weeks prior to the 1st dose of study drug until completion of the assessments and procedures scheduled during the Follow-up Visit that are known to inhibit or induce CYP3A4 isoenzymes and medications; (Refer to Appendix C: Restricted Medications). Other medications that are permitted with the approval of the investigator and sponsor include medications the patient has been stable on for at least 2 months prior to Study Day -1 of Period I and may include, but are not limited to: hormone replacement therapy, inhaled corticosteroids, thiazide diuretics, ACE inhibitors, and angiotensin II inhibitors.
2. OTC preparations that include herbal remedies and vitamin preparations from 1 week prior to the 1st dose of study drug until completion of the assessments and procedures scheduled during the Follow-up Visit unless approved by the investigator and sponsor.
3. aspirin, ibuprofen, or any other drug known to increase the propensity for bleeding are specifically prohibited from 2 weeks prior to the 1st dose of study drug until completion of the assessments and procedures scheduled during the Follow-up Visit, unless approved by the investigator and sponsor

Any medication, which is considered necessary for the subject's safety and well-being, may be given at the discretion of the investigator(s). The administration of all medication (including investigational products) must be recorded in the appropriate sections of the paper case report form (pCRF).

3.4.5.1 Concomitant medication restrictions for Cohort B and Cohort C patients

Cohort B and Cohort C patients should refrain from taking any of the following medications in addition to those listed in Section 3.4.5:

1. Tiotropium within 7 days of Study Day 1 of Period I until completion of the assessments and procedures scheduled on Study Day 5 of Period II;
2. Atrovent within 12 hours of Study Day 1 until completion of the assessments and procedures scheduled on Study Day 5 (Periods I and II);
3. Long-acting β -agonists within 72 hours of Study Day 1 until completion of the assessments and procedures scheduled on Study Day 5 (Periods I and II);
4. Short-acting β -agonists (i.e., albuterol) within 8 hours of Study Day 1 until completion of the assessments and procedures scheduled on Study Day 5 (Period I and II). These may be allowed on as needed basis with the investigator approval. However if required during an acute dyspnea episode, it is preferred that respiratory assessments as defined in Table 3 be completed first.
5. Leukotriene antagonists within 7 days of Study Day 1 of Period I until completion of the assessments and procedures on study Day 5 of Period II.
6. OTC bronchodilators (i.e., Primatine Mist) within 7 days of Study Day 1 of Period I until completion of the assessments and procedures on study Day 5 of Period II.

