The following pharmacokinetic parameters will be assessed:

Day 1: C_{max} , t_{max} , $AUC_{(0-12)}$, for AZD6140 and AR-C124910XX and the metabolite to parent C_{max} and AUC ratios.

Day 4: C_{max} , t_{max} and AUC_{τ} , for AZD6140 and AR-C124910XX, AZD6140 CL/F and the metabolite to parent C_{max} and AUC ratios.

- Pharmacodynamic

Cardiopulmonary exercise test

Minute ventilation

Spirometry (FEV_1 , FVC)

Respiratory Rate

Modified Borg Scale

Bidirectional Dyspnea Index

- Safety

Safety and tolerability will be assessed by collection of adverse events, 12-lead ECG (electrocardiogram), blood pressure, heart rate, physical examination results and laboratory assessments (chemistry, hematology, urinalysis), use of albuterol MDI.

- Genetics

Genetic analysis of the genes that are involved in absorption and disposition of, and response to AZD6140 such as the MDR-1 gene may be performed for those volunteers providing separate informed consent. The genetic samples collected from this study may be pooled with those from other studies involving AZD6140.

- Statistical methods

The respiratory parameters, and changes from baseline, will be summarized at each scheduled time point by treatment and visit for each of the cohorts using descriptive statistics. These will also be supported with graphical displays in order to ease making comparisons.

The pharmacokinetic parameters will also be descriptively summarized at each scheduled time point and treatment for the cohorts. Furthermore, graphical plots of the respiratory parameter and concentration of AZD6140 will also be explored for each of the three cohorts by visit.

Clinical Pharmacology Protocol
Study Code D5130C00028 Edition Number 1.0
Date

Safety data (adverse events, vital signs, 12-lead ECGs, laboratory data, physical examination data) will be summarized at each scheduled time point by treatment for the three cohorts using descriptive statistics.

The results of genetic analysis, if any, will be exploratory and will not be included in the clinical study report of this study.

TABLE OF CONTENTS	PAGE
TITLE PAGE.....	1
PROTOCOL SYNOPSIS.....	3
TABLE OF CONTENTS.....	7
LIST OF ABBREVIATIONS AND DEFINITION OF TERMS.....	12
1. INTRODUCTION.....	15
1.1 Background.....	15
1.2 Rationale.....	16
2. STUDY OBJECTIVES.....	17
2.1 Primary objective.....	17
2.2 Secondary objective(s).....	17
3. STUDY PLAN AND PROCEDURES.....	17
3.1 Overall study design.....	17
3.1.1 Screening/Visit 1.....	18

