6.2 Safety evaluation

6.2.1 Calculation or derivation of safety variables

Changes from baseline for the safety data (adverse events, vital signs, 12-lead ECG, physical examination data, laboratory data) will be calculated.

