6.4.3.1 Pharmacodynamic

The respiratory parameters will be descriptively summarized by treatment and listed by individual at each time point by treatment and visit for each of the cohorts using descriptive statistics. These will also be supported with graphical displays in order to ease making comparisons.

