6.4.3.4 Safety

Safety data (adverse events, vital signs, 12-lead ECGs, physical examination data, laboratory data) will be summarized at each scheduled time point by treatment for the three cohorts using descriptive statistics.

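### Albuterol use is a safety variable in the synopsis but is absent from the analysis sections, and respiratory values taken after as-needed albuterol are not set apart in the summaries for Cohorts B and C

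*Protocol*

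**What the plan says.** Section 3.4.5.1 lists short-acting beta-agonists among the drugs Cohorts B and C are to avoid, from 8 hours before Study Day 1 to the end of the Day 5 assessments in each period. It then adds "These may be allowed on as needed basis with the investigator approval". For an acute dyspnea episode, "it is preferred that respiratory assessments as defined in Table 3 be completed first".

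The synopsis, under safety variables, ends its list with "use of albuterol MDI". Section 6.2.1 reads "Changes from baseline for the safety data (adverse events, vital signs, 12-lead ECG, physical examination data, laboratory data) will be calculated", and Section 6.4.3.4 reads "Safety data (adverse events, vital signs, 12-lead ECGs, physical examination data, laboratory data) will be summarized at each scheduled time point by treatment". Neither list contains albuterol. The synopsis paragraph on statistical methods omits it too.

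For the respiratory parameters, Section 6.4.3.1 says they will be "descriptively summarized by treatment and listed by individual at each time point by treatment and visit for each of the cohorts". It makes no exception for values that follow albuterol.

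**The concern.** Rescue medication here depends on the outcome under study. Section 3.2 says the loading dose was chosen to make dyspnea as likely as possible. If the drug does provoke dyspnea or airway narrowing in patients with asthma or COPD, those patients are the likely albuterol users, and mainly in their AZD6140 period. Their later readings may then move back toward baseline, and the AZD6140 versus placebo contrast in FEV1, FVC and the dyspnea scores would shrink.

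The cohort comparison could be affected as well. Section 1.2 asks whether patients with respiratory disease are more sensitive than healthy volunteers, and Section 2.2 makes the comparison a secondary objective. The specific as-needed allowance covers Cohorts B and C only; Cohort A is reached only through the general safety clause of Section 3.4.5. Shrinkage in B and C would push that comparison toward no difference.

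Rescue use is itself a sign of a respiratory effect. As the analysis sections stand, that sign is not compared between treatments.

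**Working it through.** The protocol states no power, effect size or SD (Section 6.4.4 rests the sample size on feasibility), so there is no figure of its own to reproduce. The check has three parts.

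**1. Is albuterol use analysed?**

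| Place | Albuterol use listed? |
|---|---|
| Synopsis, safety variables | Yes |
| Synopsis, statistical methods | No |
| Section 6.2.1 | No |
| Section 6.4.3.4 | No |

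The variable is declared once and then appears in none of the analysis lists.

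**2. How many scheduled values could follow a use?** Take the 8-hour withholding interval of Section 3.4.5.1 as an example window. The protocol does not say how long albuterol alters any measurement, so 8 hours is an assumption. Table 2 puts the respiratory assessments at 2, 3, 4, 8 and 12 h after the morning dose on Days 1 and 4, and at 0 and 3 h only on Days 2 and 3.

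- Use at 2 h on Day 1: the window runs to 2 + 8 = 10 h and contains the 3, 4 and 8 h values, which is 3 of the 5 post-dose points.
- Use just after the 3 h assessment on Day 2: the next scheduled value is 24 − 3 = 21 h later, so no value falls in the window.

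The exposure is therefore real on Days 1 and 4 and small on Days 2 and 3.

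**3. How much could a cohort mean move?** All of this is illustration.

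Users: assume that every subject with dyspnea on active drug takes albuterol, with dyspnea rate p.

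- p = 20% is the approximate figure Section 3.2 gives for 400 mg.
- p = 12% comes from the 5 early reports at that dose, 5/(163/4) = 5/40.75 = 0.12, assuming four equal dose groups.
- p = 5% is an assumed low value.

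With P(at least 1) = 1 − (1 − p)^n and P(at least 2) = 1 − (1 − p)^n − np(1 − p)^(n−1):

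| p | Expected users, n = 8 | P(at least 1), n = 8 | P(at least 2), n = 8 | P(at least 1), n = 16 (B and C) |
|---|---|---|---|---|
| 5% | 0.4 | 34% | 6% | 56% |
| 12% | 0.96 | 64% | 25% | 87% |
| 20% | 1.6 | 83% | 50% | 97% |

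Attenuation: let k of 8 subjects have a fraction r of their change reversed at a time point.

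- Effect shared equally by all 8: observed/true = 1 − kr/8. For k = 2, this is 1 − 2/8 = 75% with r = 1, and 1 − 1/8 = 87.5% with r = 0.5.
- Effect only in the k users, each with change D: the true mean is kD/8 and the observed mean is kD(1 − r)/8. For k = 2, the true mean is 0.25D. The observed mean is 0 with r = 1 and 0.125D with r = 0.5.

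**The case against.** The strongest reply is that post-rescue handling is ordinary SAP content. Section 6.4.1 promises a SAP before database lock, and Section 3.4.4.2 requires evaluability decisions before the code is broken. That stands as far as it goes. A reader might infer from Section 6.4.3.1 that values after albuterol will be treated as if untreated, but the protocol does not say so; it is silent. The omission of albuterol use is different, because two analysis sections itemise the safety data and leave out a variable the synopsis declares.

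Second, the signal is partly protected. Section 3.1.2 requires the Table 3 procedures at the onset of each dyspnea episode outside the exercise test. Section 3.4.5 requires all medication to be recorded on the pCRF. Adverse events are summarised by treatment, and respiratory data are listed by individual. The concentration plots in Section 6.4.3.3 include arterial gases, which are taken only in dyspnea episodes. This also stands: the data to detect masking would largely exist. But completing Table 3 before albuterol is only a preference, and listings do not correct a cohort mean.

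Third, the pharmacodynamic set in Section 6.4.2.1 might remove affected subjects. It excludes only protocol deviations judged to affect pharmacodynamics, and albuterol given with approval is not plainly one. If it were counted as one, the subjects who reacted could be lost from the summaries altogether.

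**Conclusion.** The point holds in two parts. The omission of albuterol use from Sections 6.2.1 and 6.4.3.4 is an internal inconsistency that needs no assumption. The possible shrinkage of the effect on FEV1, FVC and the dyspnea scores in Cohorts B and C is conditional: AZD6140 must provoke symptoms, the affected subjects must take albuterol, and scheduled assessments must follow soon after. With 2 of 8 users the illustrated loss runs from 12.5% of a shared effect (half reversal) to all of an effect confined to the users (full reversal).

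Three stronger readings are not supported. Masking of the primary variables, respiratory rate and minute ventilation, is not shown, because the documents give neither size nor direction for albuterol's effect on them. The 12% reversibility figure cannot be turned into an expected shift in mean FEV1: it is part of the Cohort B entry criterion (12% or 200 mL), and Cohort C has no reversibility criterion. Nor are all assessments closely spaced, since Days 2 and 3 have only two each.

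The study is descriptive, with no formal testing (Section 6.4.3), so the consequence is a possible misreading of cohort summaries rather than a wrong test result. The correction is cheap enough to be worth making.

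**What to change.** Leave the rescue rule unchanged; whether and when albuterol is given is a clinical matter outside this point.

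- In Sections 6.2.1 and 6.4.3.4, add albuterol use (number of subjects and number of uses) by treatment and cohort, to agree with the synopsis.
- In Section 6.4.3.1, flag every scheduled respiratory value taken after albuterol within a window fixed before unblinding, for example the 8-hour withholding interval of Section 3.4.5.1. Give the summaries as measured and again without flagged values, with the number of values contributing to each.

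The second version is a check, not an unbiased estimate. If the effect sits only in the 2 users, dropping them leaves 6 subjects with a mean change of 0, so the albuterol table must be read beside it. I would not fill flagged values with the last reading before albuterol: that reading is only preferred and may not exist, and Section 3.2 reports that most dyspnea was mild and resolved with continued dosing.

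The cost is one extra set of tables, fewer values at some time points in the second version, and confirmation that the pCRF captures the clock time of each albuterol use. Section 4 already requires exact times for the pharmacodynamic measurements, but Section 3.4.5 does not mention times for medication. No study procedure is added.
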